9.1.1.1. Relationship of Adverse Events to Study Drug

For each reported adverse reaction, the participating site's PI or qualified designee must assess the relationship of the event to GRT-R910 using the following guidelines:

- Related – The AE is known to occur with the study intervention, there is a reasonable possibility that the study intervention caused the AE, or there is a temporal relationship between the study intervention and event. Reasonable possibility means that there is evidence to suggest a causal relationship between the study intervention and the AE.
- Not Related – There is not a reasonable possibility that the administration of the study product caused the event, there is no temporal relationship between the study product and event onset, or an alternate etiology has been established.

All TEAEs will be presented in a summary table for each treatment group and total by SOC, PT, and relationship to study vaccine. A separate summary will be provided for TEAEs through 28 days after GRT-R910 vaccination. If a subject has 2 or more TEAEs in the same SOC (or with the same PT) with a different relationship to study vaccine, then the subject will be counted under "Related". If the relationship information is missing, the AE will be considered related in the summary but will be presented as missing in the data listings.

9.1.1.2. Severity of Adverse Event

All AEs or SAEs will be assessed for severity, according to the toxicity grading scales in the US Food and Drug Administration (FDA) guidance document entitled “Toxicity Grading Scale for Healthy Adult and Adolescent Volunteers Enrolled in Preventive Vaccine Clinical Trials.”

For AEs not included in the protocol-defined grading system, the following guidelines will be used to describe severity. The following grades will be used in this study:

- Mild (Grade 1): Events that are usually transient and may require only minimal or no treatment or therapeutic intervention and generally do not interfere with the subject's usual activities of daily living.
- Moderate (Grade 2): Events that are usually alleviated with additional therapeutic intervention. The event interferes with usual activities of daily living, causing discomfort but poses no significant or permanent risk of harm to the research subject.
- Severe (Grade 3): Events interrupt usual activities of daily living, or significantly affects clinical status, or may require intensive therapeutic intervention. Severe events are usually incapacitating.
- Potentially Life-Threatening (Grade 4): Potentially Life-threatening refers to an AE that at occurrence represents an immediate risk of death to a subject. An event that may cause death if it occurs in a more severe form is not considered life-threatening.

All TEAEs and treatment-related TEAEs will be summarized for each treatment group and total by maximum severity, SOC, and PT. A separate summary will be provided for TEAEs through 28 days after GRT-R910 vaccination; this includes the prime dose and booster vaccination. If a subject has more than one AE on the same level (e.g., SOC or PT), the most severe AE will be summarized. If the severity information is missing, the AE will be considered Potentially Life-Threatening in the summary but will be presented as missing in the data listings.

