11.1.4.1 Severity of Adverse Events

All AEs or SAEs will be assessed for severity, according to the toxicity grading scales in the US Food and Drug Administration guidance document entitled “Toxicity Grading Scale for Healthy Adult and Adolescent Volunteers Enrolled in Preventive Vaccine Clinical Trials.”

For AEs not included in the protocol-defined grading system, the following guidelines will be used to describe severity.

Mild (Grade 1): Events that are usually transient and may require only minimal or no treatment or therapeutic intervention and generally do not interfere with the subject’s usual activities of daily living.

Moderate (Grade 2): Events that are usually alleviated with additional therapeutic intervention. The event interferes with usual activities of daily living, causing discomfort but poses no significant or permanent risk of harm to the research subject.

Severe (Grade 3): Events interrupt usual activities of daily living, or significantly affects clinical status, or may require intensive therapeutic intervention. Severe events are usually incapacitating.

AEs characterized as intermittent require documentation of onset and duration of each episode. The start and stop date of each reported AE will be recorded on the appropriate DCF. Changes in the severity of an AE will be documented to allow an assessment of the duration of the event at each level of intensity.

All SAEs will be reviewed and evaluated by the protocol study team and Gritstone, and will be sent to the EC, if required.

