4.1.3. Missing data

All data will be analyzed as collected and missing values will not be imputed or replaced.

For the classification of treatment-emergent adverse events (TEAEs) and concomitant medication, the following imputation rules will be applied in a hierarchical order:

- If no start/end date information is available (i.e., no day, month, or year is available), the event/medication will automatically be classified as a TEAE/concomitant medication/procedure. AEs with a missing start time occurring on the day of vaccination will be set to a TEAE unless the end time of the event is before the vaccination time.
- For AEs/concomitant medications if only the event start year/end year is present and the start/end year is the same or after the year of the vaccination, then the event/medication will be classified as a TEAE/concomitant medication.
- If only the event/medication start/end year and month are present and the start/end year and month is the same or after the month and year of the date of the vaccination, then the event/medication will be classified as a TEAE/concomitant medication.

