9.1.1. Unsolicited Adverse Events

Unsolicited non-serious AEs will be captured for 28 days following each GRT-R910 vaccination. Unsolicited adverse events may be recorded beyond 28 days, but only AEs occurring within 28 days of treatment vaccination will be summarized. In addition, SAEs and AESIs, including PIMMCs, MAAEs, and NOCMCs, will be captured throughout the entire study following GRT-R910 vaccination. Incidence of Unsolicited Adverse Events

An overall summary of unsolicited TEAEs through 28 days after GRT-R910 vaccination (1st dose and/or booster dose) including the number and percentage of subjects who experienced the following will be presented:

- Any unsolicited TEAEs
- Any unsolicited Treatment-Related TEAEs

- Any serious TEAEs
- Any serious Treatment-Related TEAEs
- Any unsolicited severe TEAEs
- Any Treatment-Related severe TEAEs
- Any unsolicited AESIs

An overall summary of the following AEs will be presented throughout the entire study:

- Any serious AEs
- Any unsolicited medically attended TEAEs (MAAEs)
- Any unsolicited AESIs: severe COVID-19
- Any unsolicited AESIs: PIMMCs
- Any unsolicited AESIs: NOCMs
- Any unsolicited AESIs: Serologically or Virologically Events Confirmed Relevant to COVID-19
- Any Treatment-Related AEs
- Any Treatment-Related MAAEs
- Any Treatment-Related unsolicited AESIs: severe COVID-19
- Any Treatment-Related AESIs: PIMMCs
- Any Treatment-Related AESIs: NOCMs
- Any Treatment-Related unsolicited AESIs: Serologically or Virologically Events Confirmed Relevant to COVID-19

All the categories above will be summarized by SOC and PT separately.

In addition, separate listings containing individual subject adverse event data for unsolicited AEs, unsolicited TEAEs leading to discontinuation from participation in the study or study treatment, serious AEs and unsolicited MAAEs will be provided separately.

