9.2. Clinical Laboratory Evaluations

The following tests will be performed by the local laboratory:

- Hematology:
 - White Blood Cells (WBC) Count
 - Hemoglobin (Hb)
 - Platelets (PLT)
 - Absolute Neutrophils
 - Absolute Lymphocytes
 - Absolute Monocytes
 - Absolute Eosinophils
 - Absolute Basophils
- Chemistry:
 - Alkaline phosphatase (ALP)

- Alanine aminotransferase (ALT)
- Aspartate aminotransferase (AST)
- Total bilirubin
- Creatine kinase (C)
- Serum creatinine
- Coagulation:
 - Prothrombin Time (PT)/INR
 - Activated Partial Thromboplastin Time (aPTT)
- Serology:
 - HIV
 - Hepatitis B Surface Antigen (HbsAg)
 - Hepatitis C Antibody (HCV Ab)
 - SARS-CoV-2 serology (N-specific)

Serum or urine pregnancy test - Cohort 6 only: women of childbearing potential must have a negative urine or serum pregnancy test at screening for eligibility purposes and within 24 hours prior to each study vaccination. No tables but a listing will be provided for the test. Clinical safety laboratory parameters evaluated after receipt of GRT-R910 will include WBC, Hb, PLT, ALT, AST, ALP, total bilirubin, CK, and creatinine.

Actual results and changes from baseline values for hematology and serum chemistry tests will be summarized by study days and treatment group for scheduled visits only.

A summary of toxicity grades (from 0 to 4 where 0 is Normal result (not included in the other grades), 1 is Mild, 2 is Moderate, 3 is Severe, 4 is Potentially Life-threatening) will be reported by study days and treatment group using the frequency count and percentage of subjects in each category. Toxicity grading will be performed according to FDA guidance for healthy subjects [7]. For chemistry and hematology parameters, shift in toxicity grades from baseline will be summarized by study days and treatment group using the frequency count and percentage of subjects in each category. The shift in toxicity grades will be from baseline to the worst-case post-vaccination, which will include unscheduled and repeated assessments, will also be presented. If the toxicity grade is missing for an existing lab value, then it will not be imputed, and the result will be summarized in the “Grade Missing” category. Missing grades will not be included in the overall denominator of toxicity grade summaries.

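### Unsolicited AEs with missing severity are tabulated as potentially life-threatening, so a non-serious AE with a blank grade would show as Grade 4 in the severity tables and be absent from the serious-TEAE table

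*SAP*

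**What the plan says.** SAP 9.1.1.2 sits under 9.1.1, Unsolicited Adverse Events. It summarises TEAEs by maximum severity and says: "If the severity information is missing, the AE will be considered Potentially Life-Threatening in the summary". The sentence goes on: "but will be presented as missing in the data listings". It defines the grade as follows: "Potentially Life-threatening refers to an AE that at occurrence represents an immediate risk of death to a subject".

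Protocol 11.1.4.1 grades all AEs first on the FDA toxicity scale, and then adds a fallback: "For AEs not included in the protocol-defined grading system, the following guidelines will be used to describe severity". That fallback list has three levels. The last begins "Severe (Grade 3): Events interrupt usual activities of daily living". SAP 9.1.1.2 repeats the list and adds Grade 4.

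Elsewhere the SAP treats missing values differently:

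- Section 4.1.3, the general default: "All data will be analyzed as collected and missing values will not be imputed or replaced".
- Section 9.2, laboratory grades: "If the toxicity grade is missing for an existing lab value, then it will not be imputed". Such results go into a category of their own.
- Section 9.3, vital signs: missing grades are shown as counts and left out of the denominator.

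**The concern.** Severity and seriousness are separate data items, but at Grade 4 the SAP's definition ties them together. Protocol 11.1.2 defines life-threatening in the same terms that the SAP uses for Grade 4, and both documents list a life-threatening AE among the SAE criteria. An event placed in Grade 4 by default therefore carries a label that implies an SAE, although no one has judged it to be one.

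At stake is whether the safety tables agree with each other. With about 10 subjects per cohort, a single Grade 4 count is something a safety reader will look for in the SAE table. If it came from an empty field, it will not be there, and the severity table gives no sign of why. Because the table takes each subject's worst grade, one blank also overrides every grade actually recorded for that subject at the same SOC or PT level.

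**Working it through.** **Plan's own figure.** The documents state no number on missing severity. The nearest calculation is SAP Table 3, the chance of seeing at least one event. For n = 10 and a true rate of 20% it is 1 − 0.8^10 = 89.26%, as printed. That table is not in dispute.

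**Step 1: follow one ungraded, non-serious AE through the outputs.**

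| Output | Rule | Where the AE appears |
|---|---|---|
| Tables 14.3.1.7.1 and 14.3.1.7.2, maximum severity | SAP 9.1.1.2 | Grade 4 |
| Table 14.3.1.12, serious TEAEs | Recorded seriousness (collected separately, Protocol 11.1.1) | Absent |
| AE listing | SAP 9.1.1.2 | Severity missing |

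No text changes recorded seriousness when severity is blank. The first two rows therefore disagree under the SAP's own definition of Grade 4. An SAE with a blank grade would appear in both tables.

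**Step 2: size of one blank.** Inputs are 10 planned subjects per cohort and 50 overall (SAP 4.3), Safety Analysis Set denominators (SAP 9.1) and Clopper-Pearson 95% limits as the default method (SAP 4.2). SAP 9.1.1.2 does not itself promise an interval for the severity rows, so these limits show what the default method would give.

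- For x = 0, the upper limit is 1 − 0.025^(1/n). With n = 10 it is 30.85%; with n = 50 it is 7.11%.
- For x = 1, the lower limit is 1 − 0.975^(1/n), and the upper limit p solves (1 − p)^n + np(1 − p)^(n−1) = 0.025. With n = 10 this gives 0.25% to 44.50%; with n = 50 it gives 0.05% to 10.65%.

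| Denominator | Grade 4 row with a separate 'Missing' row | Grade 4 row under the current rule |
|---|---|---|
| 10 | 0/10 = 0% (0 to 30.85%) | 1/10 = 10.0% (0.25 to 44.50%) |
| 50 | 0/50 = 0% (0 to 7.11%) | 1/50 = 2.0% (0.05 to 10.65%) |

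**Step 3: how likely is a blank?** The documents do not say. As an assumption only, take N unsolicited AEs, each left ungraded independently with probability m. The chance of at least one imputed Grade 4 entry is 1 − (1 − m)^N.

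- N = 50, m = 0.1%: 4.9%
- N = 100, m = 0.5%: 39.4%
- N = 200, m = 2%: 98.2%

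The range is too wide to support any forecast. It shows only that the result depends almost entirely on data cleaning.

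**The case against.** The best defence is that this is a deliberate, prespecified worst-case convention. SAP 9.1.1.1 has a matching rule: a missing relationship is counted as related and listed as missing. Severity assessment is required, the data system checks for incomplete entries, and missing data are queried with the sites (Protocol 15, 16.2 and 16.3), so few blanks should remain. The listings let a reader trace any that do. The laboratory analogy is also imperfect, because an ungraded laboratory result still has a measured value and an ungraded AE does not.

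Much of this stands, and it rules out several stronger readings that a reader might infer:

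- *The SAP contradicts itself on imputation.* Section 4 introduces its principles as applying unless otherwise stated, so 4.1.3 is a default and 9.1.1.2 is an exception. The further no-imputation sentence in SAP 9.1 directly follows the rule on partial dates and is most naturally read as being about dates.
- *The protocol has no Grade 4 for AEs.* Only the fallback list stops at Grade 3. By the SAP's own account in 9.1.2 and 9.2, the FDA scale used first runs to Grade 4.
- *For AEs outside the FDA scale, a Grade 4 entry could come only from a blank.* The SAP lists Grade 4 among the grades used in the study, and the eCRF options are not in the documents.
- *The imputed event would be reported as caused by the vaccine.* It reaches a treatment-related summary only if it is judged related, or if relationship is also blank.
- *Reactogenicity results or halting decisions are affected.* Solicited AEs, laboratory grades and vital-sign grades have their own sections, and neither the halting criteria nor the escalation rule refers to these tables.

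The defence does not remove the mismatch in Step 1. Counting a missing relationship as related conflicts with no other table. Counting a missing severity as an immediate risk of death does, whenever the event was recorded as non-serious.

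**Conclusion.** The point holds as a reporting fault of limited reach. For an unsolicited, non-serious AE still ungraded at analysis, the SAP's rule produces a Grade 4 entry that the serious-TEAE table does not support, and the severity table does not show that the grade was imputed. One blank in a cohort of 10 moves the Grade 4 row from 0% to 10.0%; over 50 subjects it moves from 0% to 2.0%. These figures assume full cohorts, one affected subject and no genuine Grade 4 event. If no blanks remain, the tables are unaffected.

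The rule departs from the SAP's default and from its handling of missing laboratory and vital-sign grades, and the SAP gives no reason for the difference. Separately, the four-grade list in SAP 9.1.1.2 and the three-grade fallback list in Protocol 11.1.4.1 do not match.

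A smaller ambiguity exists even with complete data. The SAP plans a line for "Any unsolicited severe TEAEs" and Tables 14.3.1.14 and 14.3.1.15 for severe events, but Severe is its label for Grade 3 alone. The documents do not say whether Grade 4 events, genuine or imputed, belong in those outputs.

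**What to change.** 1. In SAP 9.1.1.2, replace the missing-severity rule with a separate 'Missing' row in the maximum-severity tables, keeping the Safety Analysis Set denominators. State where a subject with both graded and ungraded AEs at the same level is counted; the highest recorded grade, with the ungraded events footnoted, would be simplest.
2. If a conservative view is wanted, give the worst-case count as a labelled, footnoted sensitivity row.
3. Reconcile the grade lists in Protocol 11.1.4.1 and SAP 9.1.1.2.
4. As a minor clarification, state that the severe-TEAE line and Tables 14.3.1.14 and 14.3.1.15 mean Grade 3 or higher.

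The cost is a few SAP sentences and one extra table row. The downside is a slightly less conservative primary display, which the sensitivity row offsets.

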9.1.1.3. Serious Adverse Events

An SAE will be defined as any event that includes the following outcomes:

- Death
- A life-threatening AE
- Inpatient hospitalization or prolongation of existing hospitalization
- A persistent or significant incapacity or substantial disruption of the ability to conduct normal life functions
- A congenital anomaly/birth defect

Important medical events that may not result in death, be life-threatening, or require hospitalization may be considered serious when, based upon appropriate medical judgment, they may jeopardize the patient or subject and may require medical or surgical intervention to prevent one of the outcomes listed in this definition. Examples of such medical events include allergic bronchospasm requiring intensive treatment in an emergency room or at home, blood dyscrasias or convulsions that do not result in inpatient hospitalization, or the development of drug dependency or drug abuse.

All SAEs will be recorded on the appropriate SAE DCF, will be followed through resolution or stabilization by a study clinician, and will be recorded through the end of study (EOS).

Suspected Unexpected Serious Adverse Reaction (SUSAR) will be recorded during the study. A SUSAR is any SAE where a causal relationship with the study product is at least reasonably possible but is not listed in the Investigator's Brochure (IB), Package Insert, and/or Summary of Product Characteristics.

9.1.1.4. Adverse Events of Special Interest (AESI)

For this study, protocol specified AESIs are serologically or virologically confirmed SARS-CoV-2 infection or severe COVID-19. AESIs also include the Brighton Collaboration AESIs relevant to vaccination that are listed below:

- NOCMCs – defined as any new ICD diagnosis (per current International Statistical Classification of Diseases and Related Health Problems) that is applied to the subject during the course of the study, after receipt of the study agent, that is expected to continue for at least 3 months and requires continued health care intervention.
- MAAEs – defined as hospitalization, an emergency room visit or an otherwise unscheduled visit to or from medical personnel for any reason.
- PIMMCs – These constitute a group of AEs that includes diseases which are clearly autoimmune in etiology and other inflammatory and/or neurologic disorders which may or may not have autoimmune etiology. PIMMCs that are of special interest for this study are Brighton Collaboration AESIs relevant to vaccination that include: seizures, Guillain-Barre syndrome, acute disseminated encephalomyelitis, vasculitis, anaphylaxis, vaccine associated enhanced respiratory disease, thrombocytopenia, and thrombotic events.

All AESIs will be assessed, recorded, and followed as described above under AEs.

AESIs that meet SAE criteria will be reported on a SAE form within 24 hours of the site's awareness to the Gritstone/PPD Pharmacovigilance Group. In addition, for documentation and medical assessment purposes, AESIs that do not meet SAE criteria will also be reported on an SAE form within the period for AE reporting to the Gritstone/PPD Pharmacovigilance Group; however, the narrative will indicate that the AESI did not meet SAE criteria.

9.1.1.5. Adverse Events Leading to Vaccine Dose Delay

All AEs leading to vaccine dose delay will be presented in a data listing and in general summary tables.

9.1.1.6. Adverse Events Leading to Study Discontinuation

All AEs leading to study discontinuation will be presented in a data listing and in general summary tables.

9.1.1.7. Adverse Events Leading to Study Treatment Discontinuation

All AEs leading to study treatment discontinuation will be presented in a data listing and in general summary tables.

9.1.1.8. Fatal Adverse Events

Fatal adverse events are those adverse events (also SAEs) that lead to Death according to CRF data. Fatal AEs will be presented in a data listing and in general summary tables.

9.1.2. Solicited Adverse Events

Solicited AEs are anticipated local and systemic AEs for which consistent collection of information is desired. Study clinicians will follow and collect resolution information for any reactogenicity symptoms that are not resolved within 7 days post GRT-R910 vaccination (day of vaccination and 7 subsequent days).

Solicited AEs (i.e., reactogenicity) will be collected using a memory aid and recorded on the appropriate DCF from the time of GRT-R910 vaccination within 7 days after each GRT-R910 vaccination.

For this study, solicited AEs will be:

- Injection site pain
- Injection site tenderness
- Injection site erythema
- Injection site edema/induration
- Headache
- Fatigue
- Malaise
- Myalgia
- Arthralgia
- Nausea
- Chills
- Fever

The toxicity grade for fever will be derived from temperature per FDA guidance [7]:

Vital Signs	Mild (Grade 1)	Moderate (Grade 2)	Severe (Grade 3)	Potentially Life Threatening (Grade 4)
Fever (°C)	38.0 – 38.4	38.5 – 38.9	39.0 – 40	> 40
(°F)	100.4 – 101.1	101.2 – 102.0	102.1 – 104	> 104

Temperatures will be recorded by oral thermometer and only the highest temperature will be recorded.

Reactogenicity local reactions including erythema, induration/edema, pain, and tenderness.

Reactogenicity systemic reactions including fever, chills, fatigue, malaise, myalgia, arthralgia, headache, and nausea.

Reactogenicity reactions that cannot be classified in any of the aforementioned categories for local and systemic events will be reported and summarized as unsolicited adverse events, and presented in a separate listing.

Any serious reactogenicity will be reported and summarized as serious unsolicited adverse event (SAE) (section [9.1.1.3](#)).

The number and percentage (with 95% Clopper-Pearson CIs [6]) of participants who reported any solicited AE on the vaccination day and through the 7 subsequent days (see the exact windows for each cohort in [Table 5](#)) will be tabulated by grade and treatment group for each vaccination. Percentages will be based upon the number of participants in the Safety Analysis Set within each vaccination group. Subjects will be counted once for the most severe event in cases where the subject reported more than one event per solicited AE category (e.g., injection site pain). In addition, the duration (in days) of solicited AEs after each vaccination will be summarized by treatment group for each vaccination. Duration will be calculated as the number of days of the Solicited AE during the special window ([Table 5](#)).

Table 5 Windows for solicited AEs per Cohort

Cohort	Vaccination Day	Windows for Solicited AEs
1 and 2 (Subjects NOT RECEIVING booster dose)	Day 1	Day 1 through Day 8
1 and 2 (Subjects RECEIVING booster dose)	Day 1	Day 1 through Day 8
	Day 113	Day 113 through Day 120
3, 4, and 6	Day 1	Day 1 through Day 8
	Day 29	Day 29 through Day 36

All solicited local and systemic AEs will be presented in the data listings, including a listing of solicited AEs.

Calculation of Solicited AEs duration

The number of days will be calculated at the level of subject, vaccination (prime or booster), and symptom as the longest duration of consecutive days after the injection (including the day of injection) the subjects' reported solicited AE occurs with a toxicity grade > 0. If the solicited AE continues beyond 8 days, the days from the solicited AE reported after 8 days will be included (e.g., an event that lasted 5 days in the first 8 days post injection and 4 days beyond 8 days post injection, the duration will be reported as >8 days). A separate example below illustrates how solicited AE duration is calculated:

Subject ID	Prime/Booster	Symptom	Timepoint	Severity	Grade
G0910000999	DOSE 1	Headache	Day 1	MILD	1
G0910000999	DOSE 1	Headache	Day 2	MILD	1
G0910000999	DOSE 1	Headache	Day 3	NONE	0
G0910000999	DOSE 1	Headache	Day 4	NONE	0
G0910000999	DOSE 1	Headache	Day 5	MILD	1

G0910000999	DOSE 1	Headache	Day 6	MODERATE	2
G0910000999	DOSE 1	Headache	Day 7	MODERATE	2
G0910000999	DOSE 1	Headache	Day 8	MILD	1
G0910000999	DOSE 1	Headache	Day 9	MILD	1
G0910000999	DOSE 1	Headache	Day 10	NONE	0

In the above example, the duration of the headache for the subject at dose 1 (prime dose) is 5 days. Note that there are two solicited AE episodes reported:

1. Starting Day 1 and ending Day 2 (2 days)
2. Starting Day 5 and ending Day 9 (5 days)

Only the length of the longest duration (the second episode) is considered, while the first episode is not. Each duration of episode is calculated via the formula:

$$\text{Duration}(days) = (\text{end date of Solicited AE recorded in Memory Aid}) - (\text{start date of Solicited AE recorded in Memory Aid}) + 1$$

